## 8.1 Disease Progression/Withdrawal Criteria

The reason(s) for a subject discontinuing from the study will be recorded in the electronic case report form (eCRF). A discontinuation occurs when an enrolled subject ceases participation in the study, regardless of the circumstances, prior to completion of the protocol planned schedule. The Investigator must determine the primary reason for discontinuation.

Discontinuation from the study may occur for the following reasons:

- Disease progression;

For this study, disease progression will be defined as:

- Death due to any cause
- Development of secondary MF, as evidenced e.g. by bone marrow biopsy
- Transformation into acute myeloid leukemia or myelodysplastic syndrome, as evidenced by bone marrow biopsy

- Screening failure;
- Withdrawal of patient consent;
- Severe Noncompliance;
- Worsening of the underlying disease in cases when the further participation (with dose adjustment) is not expected to provide sufficient medical care to the patient;
- Study drug-related adverse event (AE) not recovering within the pre-specified period\*;
  - pre-specified period\*: 8 weeks after discontinuation of IMP administration
- Medical condition unrelated to the underlying disease or study treatment (study drug-unrelated AE);
- Lost to follow-up.

The EoT visit will be performed at the time of study discontinuation.

In case of early treatment discontinuation, the subject should be invited to attend the safety follow-up visit (28 days after the EoT visit).

Subjects who discontinue study drug due to a study drug-related AE or abnormal laboratory value must be followed at least once a week for 8 weeks (and subsequently at 2-week intervals) until resolution or stabilization of the event. If a subject has not recovered from any toxicity within 8 weeks of prematurely discontinuing study drug, s/he must be discontinued from the study, but will continue to be followed for toxicity as described above. In this case, data will not be entered into the database but will be documented in the study log, which is stored at the site.

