4.3.4 Efficacy Variables and Analysis

4.3.4.1 Efficacy Variable

The primary efficacy endpoint is the proportion (CHR) of subjects who achieved the phlebotomy-free complete hematologic response at both month 9 and month 12 without phlebotomies during the previous 3 months. Specifically, subjects who meet all the following criteria at months 9 and 12 will be classified as responder:

- Hematocrit $<45\%$ phlebotomy-free (absence of phlebotomy during the previous 3 months)
- Platelet count $\leq 400 \times 10^9/L$,
- WBC count $\leq 10 \times 10^9/L$.

Subjects, who fails to meet all the criteria or withdraw early for any reason, will be classified as non-responder.

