4.3.4.2 Secondary Variables

- Changes in HCT, WBC, PLT and Spleen Size from baseline
 - Absolute values and changes will be computed over study timepoint (Months 3, 6, 9 and 12)
- Time to first phlebotomy
 - Time to first phlebotomy is defined as the time interval from first dosing to first time when subject experiences a phlebotomy procedure. Subjects who completed the study and never had a phlebotomy procedure will be censored at the end of the study (Month 12). Subjects who discontinued from the study prior to any phlebotomy procedure will be censored at the time of discontinuation.
- Numbers of phlebotomy
 - Number of phlebotomy procedures experienced will be categorized as 0, 1, 2, 3 and >3.
- Disease response over time (DRT)
 - DRT will be derived from hematology parameters (Hematocrit <45% without phlebotomy (at least 3 months since last phlebotomy), and platelets $\leq 400 \times 10^9/L$, and WBCs $\leq 10 \times 10^9/L$). Central laboratory assessments will be used for disease response assessment at Weeks 12, 24, 36, 52. Patients, who withdraw early for any reason, will be classified as treatment failures in visits that they did not complete. Disease response based on local laboratory assessment will be analyzed as a sensitivity analysis if the data is available.

Protocol P1101 in Japanese PV (A19-201)

- Time to first peripheral blood count response

Time to first peripheral blood count response is defined as the time interval from first dosing to first time when achieving disease response (Hematocrit <45% without phlebotomy (at least 3 months since last phlebotomy), and platelets $\leq 400 \times 10^9/L$, and WBCs $\leq 10 \times 10^9/L$). Subjects who completed the study and never achieved response will be censored at the end of the treatment (Month 12). Subjects who discontinued prior to achieving a disease response will be censored at the time of discontinuation.

- Duration of peripheral blood count response maintenance:

Duration of response maintenance will be calculated as number of days starting from assessment visit when the response was achieved till date (excluding) of assessment visit when the response was lost. If more response period occurred within one patient, the longest period will be used for analysis. Number of days will be divided by 30.5 and results presented in months. Only subjects with response will have the duration.

- Change from baseline of *JAK2* allelic burden over time

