4.3.5.5 Time to the first disease response and time to first phlebotomy

KM method will be used for estimating the distribution, median with 95% CI will be presented.

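### Time to first response censors patients who discontinue before responding; under the SAP's own rule that withdrawal is failure, the Kaplan-Meier curve then overstates the probability of responding

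*SAP*

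**What the plan says.** SAP 4.3.4.2 measures time to first peripheral blood count response from first dose to the first time the patient meets all three criteria: hematocrit below 45% with at least 3 months since the last phlebotomy, platelets at most 400 x 10⁹/L and WBC at most 10 x 10⁹/L. Completers who never respond are censored at Month 12. For those who leave early, the rule is: "Subjects who discontinued prior to achieving a disease response will be censored at the time of discontinuation".

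SAP 4.3.5.5 gives the analysis: "KM method will be used for estimating the distribution, median with 95% CI will be presented". The same sentence also governs time to first phlebotomy. No competing-risk method or sensitivity analysis is planned for either variable.

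Two other variables use the same blood-count criteria and treat withdrawal the other way:

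- Primary endpoint (SAP 4.3.4.1; SAP 2.3.1.1 agrees visit by visit): "Subjects, who fails to meet all the criteria or withdraw early for any reason, will be classified as non-responder".
- Disease response over time (SAP 4.3.4.2): "Patients, who withdraw early for any reason, will be classified as treatment failures in visits that they did not complete".

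The SAP gives no reason for the difference. SAP section 2 says that the plan follows ICH E9(R1), but no estimand is stated for time to first response.

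**The concern.** Censoring at discontinuation tells the Kaplan-Meier estimator that the patient would have gone on to respond at the same rate as those still under observation. Some of the reasons for discontinuation in Protocol 8.1 sit badly with that. Disease progression is one reason, and its definition includes "Death due to any cause". Worsening of the disease and drug-related adverse events that do not recover are others. Death rules out a later response, and the other reasons make one on study unlikely. After early discontinuation the protocol plans an end-of-treatment visit, a 28-day safety visit and follow-up of toxicity, not further response assessments.

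At stake is how a descriptive secondary result reads. A reader will take the curve as the share of treated patients who respond by a given month. If withdrawal counts as failure, that share is lower than the curve shows. With enough early losses the curve can also yield a median where fewer than half of the treated patients responded.

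**Working it through.** **The plan's own figure.** The documents give no figure for time to first response. The only figure to reproduce is the power in SAP 2.4: about 85% at Month 9 with 25 cases, a true rate of 36%, and success if the lower 95% limit exceeds 11%. With the Clopper-Pearson interval, the smallest passing count is 7 of 25 (lower limit 12.07%), and the power is 85.17%. The figure reproduces, and the point below does not touch it.

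**Inputs**

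- Response rates of 11%, 27%, 36% and 43% at Months 3, 6, 9 and 12 (SAP 2.4). These are rates at each visit in the earlier Phase 3 study. Using them as cumulative first-response rates without dropout is an assumption.
- Assessment times: "Central laboratory assessments will be used for disease response assessment at Weeks 12, 24, 36, 52" (SAP 4.3.4.2, under disease response over time). I assume that first response is read at the same visits.
- Dropout: none is stated for this trial. Protocol 5.3 reports 254 randomized and 217 completed in the earlier Phase 3 study, so 37/254 = 14.6% non-completion, both arms together. I use it as one point in a range from 0 to 30%.

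**Direction.** One minus Kaplan-Meier is never below responders divided by all treated. It is strictly above once a non-responder is censored and another patient responds later, because the censored patient has left the risk set.

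**Check A: planned rates hold without dropout.** Let d be the probability that a patient who has not responded discontinues over the four intervals, spread equally, and let s = (1 − d)^(1/4) be the probability of staying through one interval. If leaving is unrelated to later response, Kaplan-Meier recovers 43.0% at Month 12 whatever d is. The share of treated patients who actually respond on study uses the increments 11, 16, 9 and 7 points:

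0.11s + 0.16s² + 0.09s³ + 0.07s⁴

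At d = 14.6%, s = 0.9613, and the sum is 0.1057 + 0.1479 + 0.0800 + 0.0598 = 0.393. Completers without response are 0.57 × 0.854 = 0.487, so 1 − 0.393 − 0.487 = 12% of all patients leave before responding.

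| d | 1 − KM | Responders / all treated | Excess (points) |
|---|---|---|---|
| 0% | 43.0% | 43.0% | 0 |
| 5% | 43.0% | 41.8% | 1.2 |
| 10% | 43.0% | 40.5% | 2.5 |
| 14.6% | 43.0% | 39.3% | 3.7 |
| 20% | 43.0% | 37.9% | 5.1 |
| 30% | 43.0% | 35.2% | 7.8 |

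**Check B: fixed number of responders.** Take 30 patients with first responses in 3, 5, 3 and 2 of them at the four visits (13/30 = 43.3%), and vary the number who leave without response before each visit. For one loss per interval the risk sets are 29, 25, 19 and 15:

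1 − (26/29)(20/25)(16/19)(13/15) = 47.7%

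| Losses before Months 3, 6, 9, 12 | 1 − KM, Month 12 | Responders / 30 | Excess (points) |
|---|---|---|---|
| 0, 0, 0, 0 | 43.3% | 43.3% | 0 |
| 0, 1, 1, 1 | 45.9% | 43.3% | 2.6 |
| 1, 1, 1, 1 | 47.7% | 43.3% | 4.3 |
| 2, 2, 1, 1 | 51.3% | 43.3% | 8.0 |
| 2, 2, 2, 2 | 53.5% | 43.3% | 10.2 |

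**Median.** In Check A neither method reaches 50%. In Check B the curve crosses 50% with 6 losses of 30 (20%) spread as shown, and a median of about 12 months would be reported although 13 of 30 responded. Five losses spread 2, 1, 1, 1 do not cross: 1 − (25/28)(19/24)(15/18)(12/14) = 49.5%. If every loss falls before Month 3, the boundary comes sooner: four losses give 13/26 = 50.0% and five give 13/25 = 52.0%.

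**The case against.** The strongest reply is that a proportion with withdrawal as failure and a time-to-event curve censored at discontinuation answer different questions, so different handling is not in itself an error. That stands. Kaplan-Meier is valid for response had patients continued, if censoring is non-informative. What is missing is any statement that this is the question, and the SAP's other two response variables point the other way.

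Four stronger readings are tempting, and the documents do not support them.

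- **Every discontinuation rules out response.** Protocol 8.1 also lists withdrawal of consent, loss to follow-up and unrelated medical conditions, for which informative censoring is much less clear.
- **The reported median is too favourable.** At about 15% dropout spread over the year, the median is not reached under either method.
- **The curve disagrees with the visit-wise rates because of the censoring.** Disease response over time is status at each visit, and responses can be lost. A cumulative first-response curve would differ from it even with cumulative incidence.
- **The overstatement is a fixed number of points against a true 43%.** The 43% is a visit-specific rate from another study. The 14.6% counts all non-completers in both arms, including any who had already responded.

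The consequence is also limited. The variable is descriptive, with no test or success criterion. Failure-counted visit rates are already planned in SAP 4.3.5.2. An excess of 3.7 points is 0.037 × 30 = 1.1 patients, against a standard error of √(0.43 × 0.57/30) = 9 points.

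**Conclusion.** The point holds conditionally. If discontinuation before response is meant to count as failure, as it does for the primary endpoint and for disease response over time, the planned Kaplan-Meier curve for time to first response is too high by an amount that depends on dropout. In Check A the Month 12 excess is 0 points without dropout, about 1 at 5%, about 4 at 14.6% and about 8 at 30%. These figures assume that the planning rates are cumulative first-response rates without dropout, that dropout is equal across intervals among non-responders, and that the 14.6% from the earlier study is relevant here. The reported median would change only at roughly 20% dropout or more when losses are spread over the year, and sooner only if they cluster before the first assessment.

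A reader might infer that the efficacy conclusion is biased. It is not: the primary analysis already counts withdrawals as non-responders, and the stated power is unaffected. This is a minor improvement, worth making because it is cheap.

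**What to change.** In SAP 4.3.4.2, define discontinuation before response, for any reason, as a competing event for time to first response. In SAP 4.3.5.5, report the Aalen-Johansen cumulative incidence at Months 3, 6, 9 and 12 with 95% CI. An equivalent rule keeps such patients at risk to Month 12 as non-responders: with no other censoring before Month 12, the estimate is simply responders to date divided by patients treated. Give the median only if the cumulative incidence reaches 50%. Keep the current Kaplan-Meier analysis as a sensitivity analysis, labelled as estimating response had patients continued, under non-informative censoring.

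Limit the change to time to first response. SAP 4.3.5.5 covers time to first phlebotomy in the same sentence, so the two variables need separate sentences, with the phlebotomy rule left as it is.

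The cost is a short SAP edit and one more output, with no new data. Estimates become slightly less favourable, and the median may not be reached.

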4.3.5 Statistical Analyses

4.3.5.1 Primary endpoint: CHR

The CHR will be presented as number and proportion of responders who achieved CHR at BOTH Months 9 and 12 along with its 95% CI via exact method (Clopper–Pearson CI).

4.3.5.2 Disease response over time

Disease response over time (DRT) will be summarized over Months 3, 6, 9 and 12 using the same display as for CHR. The slope of the linear regression model of DRT

will be presented. These efficacy variables will be further summarized by prior HU treatment status (with or without).

4.3.5.3 Hematocrit, WBC, Platelets, and Spleen Size change over time

Values of Hematocrit <45%, Platelets count <400 x 10⁹/L, and WBC count <10 x 10⁹/L will be flagged as target values in data listings.

Count (and percentage) of patients who achieved target values (for Hematocrit, with at least 3 months since last phlebotomy) will be displayed in summary tables together with descriptive statistics. Mean profiles of the parameters will be displayed in graphs.

In listings, all local and central assessment will be presented (and clearly distinguished). In figures, only central assessments will be presented if the parameter was assessed locally and centrally at the certain visit.

Absolute values and changes from baseline will be descriptively analyzed by assessment visits.

4.3.5.4 Number of phlebotomies

Number of phlebotomies during treatment phase will be summarized using descriptive statistics and frequency/percentage for categories of 0,1,2,3 and >3.

4.3.5.5 Time to the first disease response and time to first phlebotomy

KM method will be used for estimating the distribution, median with 95% CI will be presented.

4.3.5.6 Duration of response maintenance

Duration of response maintenance will be calculated as number of days starting from assessment visit when the response was achieved till date (excluding) of assessment visit when the response was lost. If more response period occurred within one patient, the longest period will be used for analysis. Number of days will be divided by 30.5 and results presented in months.

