2.1 Study Design and Randomization

This is a Phase 2 single arm study to investigate efficacy and safety of P1101 for adult Japanese patients with PV. Eligible patients will be treated with P1101, starting at 100 μ g (or 50 μ g in patients under another cytoreductive therapy). The dose should be gradually increased by 50 μ g every two weeks (in parallel, other cytoreductive therapy should be decreased gradually, as appropriate) until stabilization of the hematological parameters is achieved (hematocrit <45%, platelets <400 x 10⁹/L and leukocytes <10 x 10⁹/L). The maximum recommended single dose is 500 μ g injected every two weeks.

At week 36 (month 9) and week 52 (month 12), the primary study endpoint, phlebotomy-free CHR, will be analyzed. After completion of the 52-week study duration, provision and administration of P1101, collection of the long-term follow up information (blood parameters, molecular and cytogenetic data, safety parameters and as also the optional bone marrow data) will be continued until the drug becomes commercially available for all study subjects.

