3.2 Study Visits/ Time-Points

Number of week and number of study visit will be included in label of study visits. The labels will be as follows: Screening, Baseline, Week 2 (V2), Week 4 (V3), Week 6 (V4), ..., Week 52 (EOT), Premature discontinuation (for End-of-Study visit of premature discontinued patients), FU (for Safety Follow-Up visit). Unscheduled visit will be labeled as 'UNS' and presented in chronological order (UNSV.c), v is visit no. and c is the times of unscheduled visit between Visit v to Visit v+1. Unscheduled visit is visit recorded as '※' in EDC.

Assessment visits will be labeled as follows: Week 12 (V7), Week 24 (V13), Week 36 (V19), Week 52 (EOT). Time-window is defined as +/- 3 days of a scheduled visit date. Deviation from the time-window will usually not be adjusted, unless specified otherwise.

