4.3.1.1 Descriptive statistics

For categorical data (e.g. response to treatment: responder) standard set of summary statistics will be counts and percentages. Missing, unknown, not available, not applicable or not done categories will be included; therefore, the percentages will be calculated of total number of patients in the set. This approach was selected because it is close to intent-to-treat principle.

For continuous data (e.g. level of lymphocytes) the following descriptive statistics will be presented: number of available observations, mean, standard deviation (SD), median, interquartile range (IQR: Q1-Q3), minimum, and maximum.

Confidence intervals will be present if appropriate.

For time-to-event data (e.g. Time to first peripheral blood count response) KM method will be used for estimating the distribution, median with 95% CI will be presented.

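### Responses still present at Week 52 have no end date under the SAP's duration rule, and duration of response has no censoring rule

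*SAP*

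**What the plan says.** Duration of response maintenance is a secondary endpoint (Protocol 7.2, SAP 2.3.2). SAP 4.3.5.6, repeated in SAP 4.3.4.2, counts days "starting from assessment visit when the response was achieved till date (excluding) of assessment visit when the response was lost", takes the longest period if a patient has several, and divides by 30.5 to give months. SAP 4.3.4.2 adds: "Only subjects with response will have the duration".

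On timing, SAP 4.3.4.2 states: "Central laboratory assessments will be used for disease response assessment at Weeks 12, 24, 36, 52". SAP 3.2 labels the same four weeks as the assessment visits, with Week 52 as end of treatment. SAP 2.1 looks further ahead ("After completion of the 52-week study duration, provision and administration of P1101, collection of the long-term follow up information"), but the SAP defines no response assessment after Week 52.

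On method, SAP 4.3.1.1 has two defaults: "For time-to-event data (e.g. Time to first peripheral blood count response) KM method will be used for estimating the distribution" and "For continuous data (e.g. level of lymphocytes) the following descriptive statistics will be presented". It does not say which covers duration. SAP 4.3.5.5 assigns Kaplan-Meier to time to first response and time to first phlebotomy. SAP 4.3.4.2 gives censoring rules for those two endpoints and none for duration. SAP 4.3.1.5 plans no imputation.

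The primary endpoint counts "responders who achieved CHR at BOTH Months 9 and 12" (SAP 4.3.5.1).

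**The concern.** The only event that closes a response period is a visit showing loss. A patient who is still responding at the last visit therefore has a start date and no end date. These are the patients in whom the treatment is working, so the rule as written drops or shortens the best outcomes and keeps those that ended in loss.

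The programmer would then have to choose between using closed periods only, cutting open periods at Week 52 and averaging, or Kaplan-Meier with some censoring date. These choices can give very different summaries of the same data, and the text allows the choice to be made after the data are seen. What is at stake is the reported durability of response.

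**Working it through.** **Inputs.** End rule, longest-period rule and the divisor 30.5: SAP 4.3.4.2 and 4.3.5.6. Assessment Weeks 12, 24, 36, 52: SAP 3.2 and 4.3.4.2. CHR rates of 11%, 27%, 36% and 43% at Months 3, 6, 9 and 12, and 30 subjects: SAP 2.4. Assumption: visits fall on their scheduled dates (SAP 3.2 allows 3 days either side).

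**Plan's own figure.** The plan gives none for duration. Its power of about 85% with 25 cases does reproduce. The exact lower 95% limit exceeds 11% from 7 responders (12.07%; 6 responders give 9.36%), and the chance of 7 or more of 25 at a 36% rate is 85.2%. Duration does not enter that calculation.

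**Step 1: apply the rule to response patterns.** Months = weeks × 7 / 30.5, so 12 weeks = 2.75, 16 = 3.67, 24 = 5.51, 28 = 6.43 and 40 = 9.18. There are 2^4 − 1 = 15 patterns with at least one response; 8 include response at Week 52 and so end open. That is a count of patterns, not a frequency. The four primary-responder patterns and one contrast (1 = in response) are:

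| Weeks 12/24/36/52 | Primary responder | Duration as written | Response already observed |
|---|---|---|---|
| 0 0 1 1 | yes | none | at least 3.67 |
| 0 1 1 1 | yes | none | at least 6.43 |
| 1 1 1 1 | yes | none | at least 9.18 |
| 1 0 1 1 | yes | 2.75 (earlier closed period) | later period at least 3.67 |
| 1 1 1 0 | no | 9.18 | 9.18, then lost |

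**Step 2: how many subjects.** Open at Week 52: 0.43 × 30 = 12.9. Primary responders must also respond at Month 9, so at most min(0.36, 0.43) × 30 = 10.8.

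**Step 3: does the choice of summary matter?** The documents give a rate at each visit, not who loses response, so any scenario has to assume that. Take 3, 8, 11 and 13 responders at the four visits (30 × the rates, rounded).

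- *Nobody loses response* (new responders 3, 5, 3, 2). As written there are no durations at all. Cut at Week 52, the mean is (3 × 9.18 + 5 × 6.43 + 3 × 3.67 + 2 × 0)/13 = 5.44 months. Kaplan-Meier shows 100% still in response.
- *One loss at each of Weeks 24, 36 and 52, each replaced* (new responders 3, 6, 4, 3; 16 ever-responders). Three first respond at Week 52 with zero follow-up, so 13 are at risk. Two assumptions about who loses:

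| | V1: one starter each from Weeks 12, 24, 36 loses at the next visit | V2: the three Week 12 starters lose |
|---|---|---|
| Closed durations | 2.75, 2.75, 3.67 | 2.75, 5.51, 9.18 |
| Mean, closed only | 9.17/3 = 3.1 | 17.44/3 = 5.8 |
| Mean, cut at Week 52 | (9.17 + 2 × 9.18 + 5 × 6.43 + 3 × 3.67)/16 = 4.4 | (17.44 + 6 × 6.43 + 4 × 3.67)/16 = 4.4 |
| Kaplan-Meier at 3.67 months | 11/13 × 10/11 = 77% | 12/13 = 92% |
| Median | not reached | 9.18 (one subject at risk) |
| Kaplan-Meier mean restricted to 9.18 months | 2.75 + 0.846 × 0.92 + 0.769 × 5.51 = 7.8 | 2.75 + 0.923 × 2.75 + 0.808 × 3.67 = 8.3 |

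In both versions the two shortcut means fall below the Kaplan-Meier restricted mean. The order of the shortcuts reverses between V1 and V2, so neither the gap nor its pattern is a fixed property of the plan. These are illustrations, not predictions.

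**The case against.** **Kaplan-Meier is arguably the default.** SAP 4.3.1.1 gives its time-to-event endpoint only as an example, and time from response to loss is naturally that kind of data. The two sibling endpoints show a convention of censoring at Month 12 or discontinuation. This is a fair reading and makes the repair short. It does not close the gap: SAP 4.3.5.5 leaves duration out, SAP 4.3.5.6 names no method, and Kaplan-Meier without a censoring date is incomplete.

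**Withdrawals are already handled.** SAP 2.3.1.1, 4.3.4.1 and 4.3.4.2 class withdrawn patients as non-responders or treatment failures at visits they miss. That stands. What is missing is whether this counts as loss for duration, and on what date.

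**Stronger readings a reader might infer.**
- That no primary responder has a duration. Not so: response, loss, response, response has a computable earlier period, although a misleading one.
- That the primary endpoint is compromised. It uses responder status at Months 9 and 12, not duration.
- That durability is understated by a known amount. Step 3 shows that the figures turn on who loses response.
- That the longest-period rule must go. It is explicit and prespecified, and censoring works with it. Replacing it with the first period would change the estimand.
- That nothing is collected after Week 52. Blood parameters are; the SAP simply does not assess response from them.

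The comparison of mean duration between two arms in Protocol 17.4.2 is a separate leftover in a single-arm trial, which the SAP does not carry over. It is not part of this point.

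**Conclusion.** The gap is real and follows from the text alone: a period ends only at an assessment visit showing loss, Week 52 is the last such visit, and nothing else supplies an end or censoring date. Applied literally, the rule ranks patients wrongly, since sustained response can score nothing while a lost response scores 9.18 months. Cutting open periods at Week 52 and averaging would instead treat ongoing response as ended.

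About 12.9 of 30 subjects would be affected, assuming that the 43% Month 12 rate from PROUD-PV applies to all 30. The direction and size of the error in the trial's actual summary cannot be derived from the documents. The endpoint is secondary and descriptive, and the CHR analysis and sample size do not change. It should be settled before database lock.

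**What to change.** In SAP 4.3.4.2 and 4.3.5.6, state that:

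- duration of response is analysed by Kaplan-Meier, with the event at the first assessment visit showing loss;
- subjects still in response are censored at their last response assessment, Week 52 at the latest;
- withdrawal while in response counts as loss at the scheduled date of the first missed assessment visit, in line with the existing treatment-failure rule, with censoring at the last assessment as a sensitivity analysis;
- the longest-period rule stays, with an open period compared at its censored length (response, loss, response, response then contributes 3.67 months, censored). A first-period analysis is optional and supportive; it would show losses that the longest period can hide;
- the output gives the proportion still in response over time, the median with 95% CI, and the number first responding at Week 52, who have zero follow-up.

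One further sentence could say how a missed central assessment without withdrawal is treated, since no imputation is planned.

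Cost: wording in two SAP sections and one Kaplan-Meier table with one sensitivity version. No new data are needed. The median may not be reached within 52 weeks.
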